#### 5.4.2.3. Combined Solicited and Unsolicited Adverse Events

A summary of subjects with all combined solicited (regardless of their duration) and unsolicited adverse events will be provided. Solicited adverse events will be coded by MedDRA as per the following codes:

Solicited symptom	Lower level term code	Corresponding Lower level term decode
Pain	10022086	Injection site pain
Erythema	10015150	Erythema
Swelling	10053425	Swelling at injection site
Fatigue	10016256	Fatigue
Fever	10016558	Fever
Gastrointestinal symptoms	10017944	Gastrointestinal disorder
Headache	10019211	Headache
Myalgia	10028411	Myalgia
Shivering	10040558	Shivering
Arthralgia	10003239	Arthralgia

For clinicaltrials.gov and EudraCT posting purposes, a summary of combined solicited and unsolicited non-serious adverse events will be produced by System Organ Class and preferred terms and according to occurrence of each event.

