#### a. **Solicited local (injection-site) adverse events**

The following local (injection-site) AEs will be solicited:

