**Table 23      Solicited local adverse events**

Pain at injection site
Redness at injection site
Swelling at injection site

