#### 5.4.2.1. **Solicited Adverse Events**

Solicited adverse events will be reported daily during the 7-day follow up period after each vaccination by the subject in the eDiaries. Missing or non-evaluatable measurements will not be replaced. The data will be made available for site follow-up on the eDiary web-portal.

In order to summarize the data, the maximum intensity of local injection site redness/swelling (in mm) and fever (in °C) will be categorized as follows

Grading	Redness/swelling	Fever
0:	≤ 20 mm	< 38.0°C
1:	> 20 - ≤ 50 mm	≥ 38.0°C - ≤ 38.5°C
2:	> 50 - ≤ 100 mm	> 38.5°C - ≤ 39.0°C
3:	> 100 mm	> 39.0°C

Fever is defined as temperature  $\geq 38.0^{\circ}\text{C}$  (regardless of the location of measurement). The preferred location for measuring temperature in this study will be the oral cavity. Body temperature will also be summarized by  $0.5^{\circ}\text{C}$  increments as follows:  $\geq 38.0, > 38.5, > 39.0, > 39.5, > 40.0^{\circ}\text{C}$ .

Each subject's data will be summarized according to the maximal severity observed during the follow-up period for each adverse event and each dose, followed by a summary across subjects and across doses.

The intensity should be assigned to 1 of the following categories:

1 (mild)	= An AE which is easily tolerated by the subject, causing minimal discomfort and not interfering with everyday activities.
2 (moderate)	= An AE which is sufficiently discomforting to interfere with normal everyday activities.
3 (severe)	= An AE which prevents normal, everyday activities. In adults, such an AE would, for example, prevent attendance at work and would necessitate the administration of corrective therapy.

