**10.1.3.6. Counting rules for combining solicited and unsolicited adverse events**

For output combining solicited and unsolicited adverse events, all serious adverse events will be considered general events since the administration site flag is not included in the expedited adverse event CRF pages.

Multiple events with the same preferred term which start on the same day are counted as only one occurrence.

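### SAP 5.4.2.3 codes solicited injection-site redness to a term that names no site, so the combined adverse event summary for public posting loses the location of that local reaction

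*SAP*

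**What the plan says.** Protocol 12.5.3 opens its list of local reactions with "The following local (injection-site) AEs will be solicited". Table 23 then gives pain, redness and swelling, each tied to the injection site; the redness entry reads "Redness at injection site". SAP 5.4.2.1 treats redness the same way when it defines grades, speaking of "the maximum intensity of local injection site redness/swelling (in mm" and so on.

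SAP 5.4.2.3 combines solicited and unsolicited events in one coded summary and states: "Solicited adverse events will be coded by MedDRA as per the following codes". In the table that follows, pain is decoded as "Injection site pain" and swelling as "Swelling at injection site". The remaining local row reads "Erythema 10015150 Erythema". The section then specifies a non-serious summary by System Organ Class and preferred term for the two public registers.

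Two other rules feed that summary. SAP 5.4.1 has unsolicited events coded from the reported verbatim to a preferred term. SAP 10.1.3.6 adds a counting rule for combined output: "Multiple events with the same preferred term which start on the same day are counted as only one occurrence".

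**The concern.** Within one table, two of three sibling events keep their location and one loses it, and the SAP gives no reason. In a table organised by System Organ Class and preferred term, the term is the only indication of where a reaction occurred. Someone reading the posted summary could not tell that the erythema line consists largely or wholly of injection-site redness, nor separate it from erythema reported elsewhere on the body.

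The distinction matters to the protocol itself. Under 12.5.7.2.2, solicited local reactions are taken as causally related without further assessment, whereas the investigator must judge causality for every other event. With about 20 subjects per group, one subject is 1/20 = 5 percentage points, so a single case on the wrong line is visible.

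**Working it through.** The plan states no figure to reproduce. The check compares the sections.

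**Step 1: identify the row.** The SAP coding table has ten rows. Seven correspond one to one with the general events of protocol Table 24 (fatigue, fever, gastrointestinal symptoms, headache, myalgia, shivering, arthralgia). The other three must be the local events of Table 23. With pain and swelling matched, the Erythema row can only be redness.

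**Step 2: compare the three local events.**

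| Protocol Table 23 | SAP row label | SAP lower level term | Site named? |
|---|---|---|---|
| Pain | Pain | Injection site pain (10022086) | Yes |
| Redness | Erythema | Erythema (10015150) | No |
| Swelling | Swelling | Swelling at injection site (10053425) | Yes |

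So 2 of 3 carry the site and 1 of 3 does not. All solicited redness reports pass through the third mapping, so all are affected in the coded summary, however many there are. The documents give no expected redness rate. In the RSV group the line could hold anything from 0/20 (0%) to 20/20 (100%) of subjects from this source.

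**Step 3: apply the counting rules to one subject** who has solicited injection-site redness and an unsolicited erythema elsewhere, assuming the latter is matched to the same preferred term.

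- Same start day, coding as written: 1 occurrence on one line (SAP 10.1.3.6). With an injection-site term for redness: 1 + 1 = 2 occurrences on two lines.
- Different start days, coding as written: 2 occurrences, but on one line and indistinguishable. With an injection-site term: 1 on each line.

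**Step 4: check whether one kind of reaction can land on two lines.** Injection-site redness can enter as unsolicited in two ways: onset outside the solicited window (protocol 12.5.4), or verbal report at a visit or call rather than through the eDiary (protocol 12.5.7). Either way it is coded from its verbatim, which may name the site. It could then sit on a different line from the solicited redness.

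**Step 5: trace which outputs use the code.** The tabulations of each solicited local event and of any-local and any-general events (SAP 5.4.1 and 5.4.2), and the grading in millimetres (5.4.2.1), are defined on the solicited events themselves. The unsolicited tables by preferred term (5.4.1) exclude solicited redness. None needs the Erythema row. Only the combined coded summary of 5.4.2.3 does.

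**The case against.** The strongest reply is that little depends on this row, and much of that stands.

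- A reader might infer that the reactogenicity profile loses redness. The documents do not support that. Redness is tabulated by group, after each dose and overall, at any grade and at Grade 3, over 7 days and again over 4 days. It is also part of a primary endpoint, and protocol 12.4.6 plans registry posting of primary and safety endpoint results, so redness should also be disclosed as a solicited local event.
- A reader might infer that a genuine erythema elsewhere would be hidden. It would not be. Unsolicited events have their own tables by preferred term with exact confidence intervals, repeated for Grade 3, related and medically attended events. Serious events are tabulated separately.
- A reader might infer that the posted table would show an apparent vaccine-related skin event. The posting summary is defined by class, term and occurrence, not by causality, and the documents do not give the System Organ Class of the code.
- The same-day collapse needs one subject, one preferred term and one start day. Nothing suggests this is likely among about 40 subjects.
- New redness with late onset is unsolicited by protocol definition, so part of the possible split is a design choice rather than a coding fault.
- Table layouts are in a separate document (SAP 10.2), so a footnote or label that restores the site cannot be excluded.

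What remains is the mapping itself. It disagrees with the protocol's name for the event, with SAP 5.4.2.1 and with its two sibling rows. SAP 10.1.3.6 implies that an administration-site flag exists outside the expedited reporting pages, but 5.4.2.3 does not use it to separate the line.

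**Conclusion.** The point holds as a limited coding error. Followed as written, SAP 5.4.2.3 places every solicited injection-site redness report under an unlocated term in the combined summary intended for public posting, on the same line as any unsolicited erythema elsewhere. The size is one of three solicited local events, in that coded output only. No primary reactogenicity percentage, confidence interval or separate unsolicited table changes.

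Loss of the site is certain under the stated rule, subject to two assumptions: that the preferred term above code 10015150 also names no site (the SAP lists lower level terms only), and that the separate table layouts do not restore it. Sharing a line in practice, the same-day collapse and the split over two lines are conditional on such events being reported. The documents give no rates for them.

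**What to change.** In the SAP 5.4.2.3 coding table, relabel the Erythema row with the protocol Table 23 name and code it to the injection-site redness or erythema lower level term, parallel to pain and swelling. The sponsor should take the term and code from the MedDRA version in use, because the documents do not supply them. Update the matching programming constant.

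The cost is one table row and one constant, with no change to data collection, visits or any other analysis, and no material downside.

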#### **5.4.2.4. Clinical Safety Laboratory Investigations**

In case of invalid or missing results or clinically significant grade 3 and above abnormal laboratory findings, a repeat testing may be done to confirm the first result (see Protocol section 12.5.6). For the analysis, the following rules will be applied:

- In general, the first result will be considered, except if this result is missing.
- In case of retesting for a grade 3 and above at pre-vaccination, the retesting will be considered if the result is < grade 3.

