**CONFIDENTIAL**

209699 (RSV OA=ADJ-003)  
Protocol Final Version 1

re-screening visit occurs. Only data from the re-screening visit, if it occurs, will be taken into consideration and recorded in the eCRF. The subject can only be randomized once the investigator receives the results and confirms the eligibility criteria.

 Any vaccination administered up to 5 years before administration of the first dose of study vaccine should be recorded in the eCRF.

 If deemed necessary by the investigator.

 Blood sampling to be performed before vaccination.

 Only re-instruction on the use of eDiary device at Visit 4.

 Intercurrent medical conditions will only be collected up to Visit 6 (Day 91); thus, not during Assessment visits for potential RSV-RTI occurring after Visit 6.

Whenever possible, the investigator should arrange study visits within the intervals described in [Table 2](#).

**Table 2** Intervals between study visits

Interval	Length of interval	Allowed interval
Screening Visit → Visit 1		3 – 30 days*
Visit 1→Visit 2	7 days	7 - 10 days
Visit 1→Visit 3	30 days	30 - 37 days
Visit 1→Visit 4	60 days	55 - 65 days
Visit 4→Visit 5	7 days	7 - 10 days
Visit 4→Visit 6	30 days	30 - 37 days
Visit 4→Phone call 1	180 days	180 - 200 days
Visit 4→Phone call 2	365 days	365 - 395 days

\* Visit 1 should take place no longer than 30 days after the Screening Visit. In case Visit 1 occurs more than 30 days after the Screening Visit, a re-screening visit should be scheduled before Visit 1 during which blood sample collection for safety laboratory assessment must be repeated (maximum one re-screening per subject is allowed). Only laboratory results from the re-screening visit, if it occurs, will be taken into consideration and recorded in the eCRF. Medical history, physical examination and review of inclusion/exclusion criteria must be repeated if a re-screening visit occurs. The subject can only be randomized once the investigator receives the results and confirms the eligibility criteria.

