In case of invalid or missing results or clinically significant abnormal laboratory findings that cannot be reasonably explained (e.g. due to a pre-existing or current medical condition), the investigator will be recommended to recall the subject in a timely manner (preferably within 7 days after investigator's awareness/assessment of the abnormal findings, if applicable) for a repeat test to confirm the result.

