### **5.4.1. Analysis of safety and reactogenicity planned in the protocol**

- The percentage of subjects with at least one local AE (solicited and unsolicited), with at least one general AE (solicited and unsolicited) and with any AE during the 7-day or 30-day follow-up period will be tabulated with exact 95% confidence interval (CI) after each dose and overall. The same computations will be done for Grade 3 AEs, for any AEs considered related to vaccination, for Grade 3 AEs considered related to vaccination and for Grade 3 non-serious AEs.
- The percentage of subjects with any AE (solicited and unsolicited) resulting in a medically attended visit during the 30-day follow-up period will also be tabulated after each dose and overall.
- The percentage of subjects reporting each individual solicited local AE (any grade and Grade 3) and solicited general AE (any grade, Grade 3, any related and Grade 3 related) during the 7-day follow-up period (i.e., on the day of vaccination and 6 subsequent days) will be tabulated for each group after each dose and overall.
- For fever, the number and percentage of subjects reporting fever by half degree (°C) cumulative increments during the 7-day follow-up period (i.e., on the day of vaccination and 6 subsequent days) will be tabulated for each group after each dose and overall. Similar tabulations will be performed for any fever with a causal relationship to vaccination and for Grade 3 ( $> 39.0^{\circ}\text{C}$ ) causally related fever. In addition, the prevalence of any and Grade 3 fever will be presented graphically over time after each vaccination.
- For each group and for each hematology and biochemistry parameter:
  - i. The percentage of subjects having hematology and biochemistry results below or above the laboratory normal ranges will be tabulated by time point.
  - ii. The summary of grading post-vaccination will be tabulated versus baseline. Grades will be based on the FDA Guidance for Industry “Toxicity Grading Scale for Healthy Adults and Adolescent Volunteers Enrolled in Preventive Vaccine Clinical Trials”, see Protocol Section 12.7 The laboratory parameters not included on FDA Toxicity Grading Scale will not be graded.

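### The SAP's laboratory retest rule does not require a replacement baseline to come from blood drawn before Dose 1

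*SAP*

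**What the plan says.** SAP 5.4.2.4 gives two rules for choosing between a first result and a repeat. The default is "In general, the first result will be considered, except if this result is missing". The exception opens with "In case of retesting for a grade 3 and above at pre-vaccination" and says that "the retesting will be considered if the result is < grade 3". Neither rule dates the repeat relative to Dose 1.

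For the repeat itself the SAP points to Protocol 12.5.6, where the investigator is advised to "recall the subject in a timely manner (preferably within 7 days after" becoming aware of the finding. That is a new blood draw on a later day.

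Safety blood is scheduled on Days 1, 8, 61 and 68, and the doses on Days 1 and 61 (Protocol 5.2). Footnote 4 to Protocol Table 1 covers the Visit 1 and Visit 4 samples: "Blood sampling to be performed before vaccination". A central laboratory tests them (Protocol 8.4.3, Table 9). Only screening or re-screening results must be in hand before randomization (footnotes to Protocol Tables 1 and 2).

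Baseline is then used in SAP 5.4.1: "The summary of grading post-vaccination will be tabulated versus baseline". Protocol Table 27 also grades hemoglobin by its change from baseline. The SAP does not define the laboratory baseline.

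**The concern.** A baseline for a vaccine safety table should be free of vaccine exposure. Here the scheduled baseline sample and the first injection fall on the same day, and nothing makes the injection wait for that result. A retest prompted by that result will therefore usually be drawn after Dose 1, yet the SAP lets it take the place of the pre-vaccination value.

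Laboratory abnormalities at Days 1, 8, 61 and 68 are part of the primary endpoint. With 20 subjects per group, one misplaced baseline is visible in a shift table. For that subject and parameter, every later comparison with baseline has the wrong reference.

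**Working it through.** The plan attaches no figure to this rule, so there is none to reproduce. The check has four steps.

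**1. Which sample the exception means.** SAP 5.3.1.1 equates pre-vaccination with Day 1, and Protocol Table 12 labels Visit 1 Pre-Vacc and the screening sample Pre-Day 1. Visit 1 is therefore the natural reading. It is not certain: Protocol Table 11 labels Visit 1 Pre-Day 1, and the Day 61 sample also precedes a dose.

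**2. When a recall retest of a Visit 1 sample is drawn.** Let t be the days from draw to the investigator's awareness (not stated; 0 to 3 assumed) and d the recall delay (0 to 7 days, the preferred period in Protocol 12.5.6). Study day of retest = 1 + t + d.

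| t (assumed) | Earliest day (d = 0) | Latest day (d = 7) |
|---|---|---|
| 0 | 1 | 8 |
| 1 | 2 | 9 |
| 2 | 3 | 10 |
| 3 | 4 | 11 |

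With t of 1 or more, every such retest follows Dose 1. Visit 2 is allowed 7 to 10 days after Visit 1 (Protocol Table 2), which is Day 8 to Day 11. The substitute baseline and the first post-dose value could therefore be drawn on the same day.

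**3. Direction of the error.**

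- *Grade 3 or higher branch.* The retest is used only if its grade is below 3, so the recorded baseline grade can only go down. For male hemoglobin in Table 27, Grade 3 is 8.5 to 10.4 g/dL and Grade 2 starts at 10.5. A first value F of at most 10.4 is replaced by a retest R of at least 10.5. For a later value Y, the fall R − Y exceeds F − Y by at least 10.5 − 10.4 = 0.1 g/dL. Later worsening looks larger.
- *Missing-result branch.* Suppose true pre-dose hemoglobin is H, the Visit 1 result is missing, and by the recall draw and Day 8 it has fallen by 2.3 g/dL (illustrative). Against H the change is 2.3, Grade 3 by change (2.1 to 5.0 in Table 27). Against the recalled value it is (H − 2.3) − (H − 2.3) = 0. The effect is absorbed.
- *Erroneous Visit 1 value.* If the true pre-dose grade was 0, the laboratory reported Grade 3, and the retest shows a vaccine-induced Grade 1 or 2, then that Grade 1 or 2 becomes baseline and the shift from Grade 0 is lost.

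**4. The difference between time points.** The exception covers pre-vaccination results only. Let q be the chance of a Grade 3 or higher first result, equal before and after vaccination (no vaccine effect). Assume that all such results are retested and that a retest is below Grade 3 with chance r. Expected counts per 20 subjects are 20 × q × (1 − r) at baseline and 20 × q after vaccination.

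| q | r = 25% | r = 50% | r = 75% | After vaccination |
|---|---|---|---|---|
| 5% | 0.75 | 0.50 | 0.25 | 1.00 |
| 10% | 1.5 | 1.0 | 0.5 | 2.0 |

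The same formula applies to both groups.

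**The case against.** Five objections deserve weight.

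- **The rule does not generally hide harm.** A reader might infer that a post-dose baseline masks or reverses a vaccine effect. In the Grade 3 or higher branch it does the opposite (step 3). Masking is confined to a missing or erroneous Visit 1 value. This stands.
- **The one-sidedness is defensible.** A reader might infer from step 4 that the rule manufactures shifts to Grade 3. Keeping an unconfirmed post-vaccination Grade 3 result prevents a later normal value from erasing a signal. The rule applies equally to both arms of a randomized study that is described relative to placebo, so without a vaccine effect the expected excess is the same in each. This stands, and no change is needed there.
- **The timing is inferred.** No turnaround is stated, and a same-day result could precede the injection. If the exception was meant for screening retests, those would precede Dose 1. This stands as a limit on certainty; the text still contains no safeguard.
- **It will be rare.** Subjects are screened 3 to 30 days earlier, and for most parameters out-of-range values exclude them unless judged not clinically significant (Protocol 6.2.1). Recall is only recommended. Zero affected subjects is plausible. This stands.
- **Few outputs depend on baseline.** Post-vaccination percentages outside the normal range do not use it. Holding rule 2d counts Grade 3 or higher abnormalities up to the Day 8 visit and names no baseline; hemoglobin graded by change would be the only link. This largely stands.

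**Conclusion.** The defect is real but narrow. As written, SAP 5.4.2.4 permits blood drawn after Dose 1 to serve as the pre-vaccination laboratory value. For a recall retest of a Visit 1 sample this always happens if turnaround is a day or more, which is an assumption because the documents are silent. The SAP does not state this result outright; it follows from reading its rule with the protocol's sampling and recall provisions.

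The damage is limited to the retested parameter: its row in the grade-versus-baseline table and, for hemoglobin, the change grade. The direction depends on the branch: more apparent worsening when a Grade 3 or higher value is replaced, and possible absorption of an early effect when Visit 1 is missing or wrong. The number affected cannot be derived from the documents; it is likely to be few and may be none. Each is 1/20 = 5% of an arm. The documents do not support a claim that the rule systematically conceals harm or favors the vaccine.

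**What to change.** Add to SAP 5.4.2.4:

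- Laboratory baseline is, for each parameter, the last valid result from blood drawn before Dose 1: the Visit 1 sample or, if that result is missing or invalid, the screening (or re-screening) sample.
- A retest from blood drawn after Dose 1 is never used as baseline. A rerun of the Visit 1 tube remains acceptable, since that blood was drawn before the dose.
- State which visit the word pre-vaccination refers to in the exception. Also state when a result counts as invalid, decided without knowledge of treatment group: the section names invalid results as a reason to repeat, but replaces only missing ones.

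The rule for post-vaccination results can stay. Whether first and repeat values will be listed cannot be judged here, because the list of tables and listings is a separate document (SAP 10.2).

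The cost is SAP wording only. Hematology and biochemistry are already measured and recorded at screening, and no visit, sample or procedure changes. There are two small downsides: a screening value may be 3 to 30 days old, and a valid but transient Grade 3 result at Visit 1 would remain the baseline.
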